### 8.3.2. Unsolicited Adverse Events

Overall number of subject experiencing unsolicited AEs, including SAEs, onset during the first 28 days after each dose vaccination will be summarized by vaccine groups and relatedness ([Table 41](#)). Number of subject experiencing SAEs throughout the entired study period will also be presented ([Table 42](#)). All unsolicited AEs with onset during the first 28 days following each dose administration will be assessed for severity and as either related or not related to study product by the investigator ([Table 43](#) and [Table 44](#)).

AESI, MAAEs, and SAEs: All AESI, MAAEs, and SAEs through Visit 7 (Day 197) will be recorded and the number, severity, and relatedness to study product will be summarized ([Table 45](#) through [Table 49](#)). Subject-wise data listing for all unsolicited AEs will be provided ([Listing 7](#)).

When an AE occurs more than once for a subject, the subject will be counted only once for the corresponding PT according to the maximum severity of the events.

Medically-attended adverse events (MAAEs) are unsolicited AEs for which the subject received medical attention, such as during an emergency room visit or a visit to or from medical personnel (e.g., medical doctor).

Adverse events of special interest (AESIs) for this study include:

- Potential immune-mediated medical condition (PIMMC), given that vaccination has been associated with autoimmunity
- AEs associated with COVID-19, given the importance of subject safety of managing any occurrence of COVID-19, and the possible association of vaccination with enhancement of COVID-19

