## 3.2. Study Endpoints

### 3.2.1. Primary Endpoints

#### Safety and Tolerability

- Number and severity of solicited local and systemic AEs during the first 7 days after each vaccination
- Number, severity, and relatedness of clinically significant hematological and biochemical measurements at 7 days post each vaccination
- Number, severity and relatedness of all unsolicited AEs during the first 28 days after each vaccination
- Number, severity and relatedness of SAEs throughout the entire study period
- Number, severity and relatedness of MAAEs throughout the entire study period
- Number, severity and relatedness of AESI throughout the entire study period, including AESI relevant to COVID-19, and potential immune-mediated medical conditions (PIMMC)

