**3.3.10. Causal Relationship of an Adverse Event**

A suspected adverse drug reaction (ADR) means any AE for which there is a reasonable possibility that the study vaccine caused the AE. A reasonable possibility means there is evidence to suggest a causal relationship between the vaccine and the AE. All cases judged by either the PI/designee or the Sponsor as having a reasonable suspected causal relationship to the study vaccine will qualify as ADRs. Medical judgment will be used to determine the relationship, considering all relevant factors, including pattern of reaction, temporal relationship, confounding factors such as concomitant medication, concomitant diseases, and relevant history.

The likelihood of the relationship of the AE to study vaccine is to be recorded as follows:

- Related: There is a reasonable causal relationship between the vaccine administered and the AE.
- Not Related: There is no reasonable causal relationship between the vaccine administered and the AE.

Note: solicited reactogenicity events will not be judged for relatedness.

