## **6.6. Interim Analyses and Data Monitoring**

### **6.6.1. Interim Analysis**

Interim analyses will be performed after the last subject in the first phase has completed Visit 6 (Day 57) assessments and all the results are available. At the time of the interim analysis, safety results (unblinded to the DSMB only) and immunogenicity results (unblinded at group level only) will aid in the selection of formulations to evaluate in the second phase of the study. The interim report will include Tables 4-5, 8-11, 17, 29, 31, 34, 36, 39-42, 60, 64 and 90-119 as well as Listings 7-9.

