## Appendix 1.D. Adverse Events

**Table 39: Overall Number of Subjects with Non-Serious Adverse Events from Combined Solicited and Unsolicited Adverse Events Onset during the First 28 days after each Vaccination in Safety Analysis Population**

	All (N = 120)	COVIVAC				Placebo (N = 20)
		1 µg (N = 25)	3 µg (N = 25)	10 µg (N = 25)	1 µg + CpG (N = 25)	
		n (%) (95% CI*)	n (%) (95% CI*)	n (%) (95% CI*)	n (%) (95% CI*)	
Overall, n (%)						
with one or more adverse events	xx (xx.x%) (xx.x-xx.x)					
with no adverse event						
with vaccine-related adverse events						
After 1st Dose Vaccination						
with one or more adverse events						
with no adverse event						
with vaccine-related adverse events						
After 2nd Dose Vaccination						
with one or more adverse events						
with no adverse event						
with vaccine-related adverse events						

**Note:** \*Two-sided 95% CIs computed via the Clopper-Pearson method

**Table 40: Summary of Non-Serious Adverse Events from Combined Solicited and Unsolicited Adverse Events Onset during the First 28 days after each Vaccination by MedDRA term in Safety Analysis Population**

System Organ Class (SOC)	Preferred Term (PT)	All (N = 120)		COVIVAC								Placebo (N = 20)	
				1 µg (N = 25)		3 µg (N = 25)		10 µg (N = 25)		1 µg + CpG (N = 25)			
		NE	n (%)	NE	n (%)	NE	n (%)	NE	n (%)	NE	n (%)	NE	n (%)
Overall													
All SOC	All PT	x x	xx (xx.x %)	xx	xx (xx.x %)	xx	xx (xx.x %)	xx	xx (xx.x %)	xx	xx (xx.x %)	xx	xx (xx.x %)
SOC 1	All PT 1 PT 2												
SOC 2	All PT 1 PT 2												
1st Dose													
All SOC	All PT												
SOC 1	All PT 1 PT 2												
SOC 2	All PT 1 PT 2												
2nd Dose													
All SOC	All PT												
SOC 1	All PT 1 PT 2												
SOC 2	All PT 1 PT 2												

**Note:** “N” is the total number of subject in each group and “xx” represent the value number.

“NE” is number of events.

“n” is number of subject who has at least one adverse event.

**Table 41: Overall Number of Subjects with Adverse Events Onset during the First 28 days after each Vaccination in Safety Analysis Population**

	All (N = 120)	COVIVAC				Placebo (N = 20)
		1 µg (N = 25)	3 µg (N = 25)	10 µg (N = 25)	1 µg + CpG (N = 25)	
		n (%) (95% CI*)	n (%) (95% CI*)	n (%) (95% CI*)	n (%) (95% CI*)	
Overall Adverse event, n (%)						
with one or more adverse events	xx (xx.x%) (xx.x-xx.x)					

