with vaccine-related AESIs								
withdrawn due to an AESI								
2nd Dose Vaccination								
with one or more AESIs								
Potential immune-mediated medical conditions (PIMMC)								
Associated with COVID-19								
with no AESI								
with vaccine-related AESIs								
withdrawn due to an AESI								

**Note:** “N” is the total number of subject in each group and “xx” represent the value number.

**Table 42: Overall Number of Subjects with Serious Adverse Events throughout the Entire Study Period in Safety Analysis Population**

	All (N = 120)	COVIVAC				Placebo (N = 20)
		1 µg (N = 25)	3 µg (N = 25)	10 µg (N = 25)	1 µg + CpG (N = 25)	
		n (%) (95% CI*)	n (%) (95% CI*)	n (%) (95% CI*)	n (%) (95% CI*)	
with one or more serious adverse events	xx (xx.x%) (xx.x-xx.x)					
with no serious adverse event						
with vaccine-related serious adverse events						
with medically-attended serious AE (MAAEs)						
with serious adverse events of special interest (AESI)						
Potential immune-mediated medical conditions (PIMMC)						
Associated with COVID-19						
withdrawn due to a serious adverse event						
SAEs leading to death						

**Note:** “N” is the total number of subject in each group and “xx” represent the value number.

**Table 43: Number of Subjects with Serious Adverse Events Onset during the First 28 days after each Vaccination by Severity**

	All (N = 120)	COVIVAC				Placebo (N = 20)
		1 µg (N = 25)	3 µg (N = 25)	10 µg (N = 25)	1 µg + CpG (N = 25)	
1st Dose Vaccination						
with one or more serious adverse events by severity*	xx (xx.x%)	xx (xx.x%)	xx (xx.x%)	xx (xx.x%)	xx (xx.x%)	xx (xx.x%)
Grade1 (Mild)	xx (xx.x%)	xx (xx.x%)	xx (xx.x%)	xx (xx.x%)	xx (xx.x%)	xx (xx.x%)
Grade2 (Moderate)	xx (xx.x%)	xx (xx.x%)	xx (xx.x%)	xx (xx.x%)	xx (xx.x%)	xx (xx.x%)
Grade3 (Severe)	xx (xx.x%)	xx (xx.x%)	xx (xx.x%)	xx (xx.x%)	xx (xx.x%)	xx (xx.x%)
Grade4 (Potentially life-threatening)	xx (xx.x%)	xx (xx.x%)	xx (xx.x%)	xx (xx.x%)	xx (xx.x%)	xx (xx.x%)
with no serious adverse event	xx (xx.x%)	xx (xx.x%)	xx (xx.x%)	xx (xx.x%)	xx (xx.x%)	xx (xx.x%)
with vaccine-related serious adverse events by severity*	xx (xx.x%)	xx (xx.x%)	xx (xx.x%)	xx (xx.x%)	xx (xx.x%)	xx (xx.x%)
Grade1 (Mild)	xx (xx.x%)	xx (xx.x%)	xx (xx.x%)	xx (xx.x%)	xx (xx.x%)	xx (xx.x%)
Grade2 (Moderate)	xx (xx.x%)	xx (xx.x%)	xx (xx.x%)	xx (xx.x%)	xx (xx.x%)	xx (xx.x%)
Grade3 (Severe)	xx (xx.x%)	xx (xx.x%)	xx (xx.x%)	xx (xx.x%)	xx (xx.x%)	xx (xx.x%)

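### Two of the six primary safety endpoints are not fully tabulated as defined (unsolicited AE severity; clinical significance and relatedness of post-dose labs), and the interim report drops solicited severity

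*SAP*

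**What the plan says.** Safety and tolerability form the only primary objective, and SAP section 3.2.1 lists six primary endpoints. Three matter here:

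- Solicited events: "Number and severity of solicited local and systemic AEs during the first 7 days after each vaccination".
- Laboratory: "Number, severity, and relatedness of clinically significant hematological and biochemical measurements at 7 days post each vaccination".
- Unsolicited events: "Number, severity and relatedness of all unsolicited AEs during the first 28 days after each vaccination".

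For the unsolicited endpoint, section 8.3.2 states "All unsolicited AEs with onset during the first 28 days following each dose administration will be assessed for severity and as either related" or not, and points to Tables 43 and 44. The first of these in Appendix 1.D is "Table 43: Number of Subjects with Serious Adverse Events Onset during the First 28 days after each Vaccination by Severity"; Table 44 is the same count over the whole study.

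For the laboratory endpoint, section 8.3.1 says Tables 60 to 68 break results down by grade, relatedness and group. Section 8.6 adds a summary of clinically significant values. It treats Grade 2 and above as automatically significant and reportable as an AE, and leaves Grade 1 to the investigator.

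For the interim, section 6.6.1 states: "The interim report will include Tables 4-5, 8-11, 17, 29, 31, 34, 36, 39-42, 60, 64 and 90-119 as well as Listings 7-9".

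On causality, section 3.3.10 carries the remark "Note: solicited reactogenicity events will not be judged for relatedness". Table 39, which pools solicited and unsolicited non-serious events, nevertheless has the row "with vaccine-related adverse events".

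**The concern.** A primary endpoint should lead to an output that reports it by arm. Here the cross-reference for unsolicited severity leads to tables restricted to serious events. The laboratory shells lack two elements that the text says they contain. The interim report, which supports the choice of two formulations, shows how often solicited reactions occur but not how severe they are.

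At stake is the comparison of the 1, 3 and 10 µg arms and the adjuvanted arm. Incidence alone cannot separate an arm whose reactions are mostly Grade 1 from one with the same frequency at Grade 3. A programmer following the shells literally would also produce a final report with no by-arm count of ordinary non-serious unsolicited events by grade.

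**Working it through.** No power, rate or threshold enters this point, so the check is a trace from each endpoint in section 3.2.1 to the table cited for it, and then to that table's rows.

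| Primary endpoint | Tabulated by arm in the final report | Missing from tables |
|---|---|---|
| Solicited AEs | 29, 31, 34, 36 (incidence); 30, 32, 35, 37 (severity) | nothing |
| Clinically significant labs | 60, 64 (any abnormality); 61-63, 65-68 (normal/abnormal and grade) | clinical significance; relatedness |
| Unsolicited AEs | 41, 56 (number, relatedness); 50 (by MedDRA term) | severity |
| SAEs | 42-44, 51, 57 | nothing |
| MAAEs | 45 | nothing |
| AESI | 46-48 | nothing |

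Two of six endpoints therefore have a gap in the final report and four do not.

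**Unsolicited severity.** Going through Tables 39 to 59:

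- 39-41, 50, 54, 56 and 58 have no grade rows.
- 42-44, 51-53, 55, 57 and 59 are confined to serious events.
- 45-48 give grades for medically attended events, AESI and immune-mediated conditions only.
- 49 uses grade, but its cells are mean duration in days, not counts.

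Tables counting all unsolicited AEs by grade and arm: 0. A non-serious Grade 2 or 3 event that is neither medically attended nor an AESI is never counted by grade. The rule in 8.3.2 that a subject counts once at maximum severity has no all-unsolicited table to act on.

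**Laboratory.** Tables 60 to 68 are 68 − 60 + 1 = 9 shells. Those with a relatedness row: 0 of 9. Those with a clinical-significance row: 0 of 9. Tables 25 and 27 do count clinically significant results, but at screening only. Because Grade 2 and above is automatically significant, that part of the count can be read from the moderate, severe and life-threatening rows of Tables 61-63 and 65-68. Grade 1 values judged significant cannot be separated from other Grade 1 values. Relatedness of laboratory findings cannot be recovered by arm from the AE tables either: Table 56 has relatedness without preferred terms, and Table 50 has preferred terms without relatedness.

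**Interim list.** Solicited incidence tables included: 4 of 4 (29, 31, 34, 36). Solicited severity tables included: 0 of 4 (30, 32, 35, 37). Listing 6 in Appendix 3 holds solicited reactions with grade; the list starts at Listing 7, which Appendix 3 assigns to unsolicited events. Section 8.3.1 calls the solicited listing Listing 7, while section 8.3.2 uses the same number for unsolicited events, so one of the two citations is wrong. Laboratory grade and unsolicited grade do reach the interim by subject, through Listings 9 and 7.

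**Table 39 (minor).** Solicited events are not judged for relatedness, and no rule says whether they enter the related row. Two programmers could fill it differently.

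**The case against.** The strongest reply is that most of the information exists. Four endpoints are fully tabulated. Relatedness of unsolicited events is in Tables 41 and 56, and grade and relationship for each event are in Listing 7, which is in the interim package. Medically attended events are by definition unsolicited and are graded in Table 45. Section 8.6 already commits in text to a clinically significant summary, and the preface calls the shells samples. Clinically significant labs are recorded as AEs, so they also enter the AE tables. All of this stands, and it narrows the point to the severity dimension of unsolicited AEs and to two row types in the laboratory shells. It does not close the gap: a subject listing is not a summary by arm, and the text in 8.3.1 and 8.3.2 names specific tables that do not contain what is promised.

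On the interim, a reader might infer that the DSMB would be kept from seeing severity, or that the sponsor would compare unblinded safety by arm. The SAP supports neither. Section 6.6.2 has the DSMB review unblinded safety data through Day 57 without limiting it to the listed tables. Section 6.6.1 restricts unblinded safety to the DSMB, and under section 4.1 the sponsor works from the DSMB recommendation together with immunogenicity. The safety review team also sees new Grade 3 solicited events, blinded. The listing misnumbering also means the solicited listing may have been intended for the interim. What remains is that the specified report, which also goes to the ethics board and the ministry, has no solicited severity table, although section 4.1 names solicited events among the down-selection inputs.

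Table 39 is a supplementary pooled table, and each solicited reaction is shown separately in Tables 29, 31, 34 and 36. That part is a labelling matter.

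**Conclusion.** The point holds in this bounded form. Two of six primary safety endpoints are not fully tabulated as defined, and a third, solicited events, loses its severity component in the interim report. The size is: no table of all unsolicited AEs by grade and arm; 0 of 9 post-dose laboratory shells with clinical significance or relatedness; and 0 of 4 solicited severity tables in the interim list.

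A reader might go further and conclude that these endpoints cannot be reported. That does not follow, because the data are planned, much is tabulated elsewhere, and Grade 2 or higher laboratory values can be inferred from the grade rows. No population, estimator, interval method or advancement threshold is affected. It should be fixed as an inconsistency between text and shells; it is not a flaw in the analysis method.

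The conclusion assumes that the shells and the interim list are followed as written, that Appendix 3 governs listing numbers, and that Table 56, whose title does not say so, covers unsolicited events as 8.3.2 says Table 41 does.

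**What to change.** 1. Add a table of unsolicited AEs within 28 days of each dose, by arm, maximum grade and relatedness, and cite it in 8.3.2; keep Tables 43 and 44 for serious events.
2. Add clinically significant and relatedness rows at Day 8 and Day 36 to the laboratory tables.
3. Add Tables 30, 32, 35, 37 and Listing 6 to the interim list in 6.6.1, and correct the solicited listing number in 8.3.1 from 7 to 6.
4. Restrict the related row in Table 39 to unsolicited AEs and label it so.

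The cost is one new shell, extra rows in existing laboratory shells, an edited interim list, one corrected listing number and one row label. Everything comes from data the plan already collects; there are no new assessments and no change to sample size or timing.

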### 8.4. Deaths, Serious Adverse Events and Other Significant Adverse Events

A listing of all data related to deaths, SAEs and other significant AEs will be presented (See

[Appendix 1.D., Listing 8\).](#)

## 8.5. Pregnancies

All WOCBP will be monitored for pregnancy during the study and for the use of adequate contraception until completion of Visit 6 (Day 57). If a female subject becomes pregnant after Visit 1 (Day 1) but prior to Visit 3 (Day 29), no further study product will be administered. The subject will be encouraged to complete all remaining study visits for safety assessments alone, and if possible and agreed to by the subject, continue to be followed through the pregnancy outcome. The pregnancy and its outcome will be documented, even if birth occurs after the scheduled end of the study for the subject.

## 8.6. Clinical Laboratory Evaluations

Screening viral serology assessments for Hepatitis B (HBsAg) and Hepatitis C (HCV Ab) will be described as categorical variables on a demographics table ([Table 28](#)).

Clinical safety laboratory values (serum hematology and chemistry) are collected at screening and 7 days post-vaccination for each dose. They will be summarized for the safety analysis population. Hematology and chemistry results evaluated at screening will be summarized as continuous variables by vaccine groups ([Table 24](#) through [Table 27](#)).

Screening and post-vaccination (Day 8 and Day 36) serum hematology and chemistry will be graded by severity. Grade 2 or higher were automatically considered as clinically significant and reported as AE, while Grade 1 abnormalities were subject to investigator opinion.

Continuous summaries of laboratory parameters (Hgb, WBC count, Plt, AST, ALT, total bilirubin, and creatinine) and the change from baseline will be computed by time point (including unscheduled visits, in chronological order) and treatment group, including mean, standard deviation, median, 1st and 3rd quartiles (IQR) and range, for all observations regardless of abnormality status (see [Table 60](#) through [Table 68](#)). Summaries will also be produced presenting the proportion of each severity grading using the number of subjects that provided a sample as denominator, as well as those considered clinically significant, using the maximum severity for a given subject, where relevant. A summary of safety laboratory abnormalities will be prepared by parameter, severity (by grade and any abnormality), and time point. Fisher's exact 2-tailed test will be used to test the differences in abnormality rates across all groups, by time point for scheduled visits, and overall.

Figures will be prepared for each laboratory parameter using boxplots to describe the distribution of values and changes from baseline across visits, by group, incorporating unique points and/or colors for abnormalities ([Figure 2](#) through [Figure 8](#)).

A listing of all lab results will be prepared, in addition to a listing only for abnormalities, and each will include the parameter, study day (Visit), value, units, change from baseline, LLN/ULN, and abnormality grade ([Listing 9A](#), [Listing 9B](#), Appendix 3).

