### **3.3.7. Treatment-Emergent Adverse Event**

A treatment-emergent AE is defined as an AE that is not present prior to administration of the study product, or, if present prior to the administration of the study medication, increases in intensity after administration of the study medication during the course of the study.

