### 4.2.2. Inclusion Criteria for Enrollment

Participants are eligible for Phase 1 study if they fulfill the inclusion criteria below:

- Adult 18 through 59 years of age inclusive at the time of randomization.
- Healthy, as defined by absence of clinically significant medical condition, either acute or chronic, as determined by medical history, physical examination, screening laboratory test results, and clinical assessment of the investigator.
- Has provided written informed consent prior to performance of any study-specific procedure.
- Has a body mass index (BMI) of 17 to 40 kg/m^2, inclusive, at screening.
- Resides in study site area and is able and willing to adhere to all protocol visits and procedures.
- If a woman is of childbearing potential, must not be breastfeeding or be pregnant (based on a negative urine pregnancy test at screening and during the 24 hours prior to receipt of the first dose of IP), must plan to avoid pregnancy for at least 28 days after the last dose of IP, and be willing to use an adequate method of contraception consistently and have a repeated pregnancy test prior to the second (last) dose of IP.

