### 4.2.3. Exclusion Criteria for Enrollment

Participants will be ineligible for this study for any of the following conditions or reasons:

- Use of any investigational medicinal product within 90 days prior to randomization or planned use of such a product during the period of study participation.
- History of administration of any non-study vaccine within 28 days prior to administration of study vaccine or planned within 3 months after enrolment.

**Note:** receipt of any COVID-19 vaccine that is licensed or granted Emergency Use Authorization in Vietnam during the course of study participation is not exclusionary if administered after Visit 5.

- Previous receipt of investigational vaccine for SARS or MERS, or any investigational or licensed vaccine that may have an impact on interpretation of the trial results.
- History of hypersensitivity reaction to any prior vaccination or known hypersensitivity to any component of the study vaccine.
- History of egg or chicken allergy.
- History of angioedema.
- History of anaphylaxis.
- Acute illness (moderate or severe) and/or fever (body temperature measured orally  $\geq 38^{\circ}\text{C}$ ).
- Any abnormal vital sign deemed clinically relevant by the PI.
- Abnormality in screening laboratory test deemed exclusionary by the PI in consultation with the Sponsor.
- A positive serologic test for hepatitis B (HBsAg) or hepatitis C (HCV Ab).
- History of laboratory-confirmed COVID-19 (RT-PCR positive to SARS-CoV-2).
- History of confirmed HIV.
- History of laboratory-confirmed COVID-19.
- History of malignancy, excluding non-melanoma skin and cervical carcinoma in situ.
- Any confirmed or suspected immunosuppressive or immunodeficient state.
- Administration of immunoglobulin or any blood product within 90 days prior to first study injection or planned administration during the study period.
- Administration of any long-acting immune-modifying drugs (e.g., infliximab or rituximab) or the chronic administration (defined as more than 14 days) of immunosuppressants within six months prior to first study injection, or planned administration during the study period (includes systemic corticosteroids at doses equivalent to  $\geq 0.5$  mg/kg/day of prednisone; the use of topical steroids including inhaled and intranasal steroids is permitted).
- History of known disturbance of coagulation or blood disorder that could cause anemia or excess bleeding (e.g, thalassemia, coagulation factor deficiencies).

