**Table 25: Abnormality of Hematology Test with Clinically Significant Result at Screening**

	All (N = 120)	COVIVAC				Placebo (N = 20)
		1 µg (N = 25)	3 µg (N = 25)	10 µg (N = 25)	1 µg + CpG (N = 25)	
		n (%)	n (%)	n (%)	n (%)	
Hemoglobin (g/dL)	xx (xx.x%)	xx (xx.x%)	xx (xx.x%)	xx (xx.x%)	xx (xx.x%)	xx (xx.x%)
White Blood Cell (WBC) (x 10  /µL)						
Platelets (x 10  /µL)						

**Note:** + CpG1018 1.5 mg (Adjuvant)

“xx” represent the value number.

Only subjects with abnormality of hematology result will be considered in this table.

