**Table 27: Abnormality of Chemistry Test with Clinically Significant Result at Screening**

	All (N = 120)	COVIVAC					Placebo (N = 20)
		1 µg (N = 25)	3 µg (N = 25)	10 µg (N = 25)	1 µg + CpG (N = 25)		
		n (%)	n (%)	n (%)	n (%)		
Creatinine (mg/dL)	xx (xx.x%)	xx (xx.x%)	xx (xx.x%)	xx (xx.x%)	xx (xx.x%)	xx (xx.x%)	xx (xx.x%)
ALT (U/L)							
AST (U/L)							
Total bilirubin (mg/dL)							

**Note:** + CpG1018 1.5 mg (Adjuvant)

“xx” represent the value number.

Only subjects with abnormality of chemistry result will be considered in this table.

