## Appendix 1.E. Hematology Results

**Table 60: Overall Number of Subjects with Any Abnormal Hematology Results in Safety Analysis Population**

	All (N = 120)	COVIVAC				Placebo (N = 20)
		1 µg (N = 25)	3 µg (N = 25)	10 µg (N = 25)	1 µg + CpG (N = 25)	
Overall, n (%)						
with hemoglobin abnormal result	xx (xx.x%)	xx (xx.x%)	xx (xx.x%)	xx (xx.x%)	xx (xx.x%)	xx (xx.x%)
with WBC abnormal result	xx (xx.x%)	xx (xx.x%)	xx (xx.x%)	xx (xx.x%)	xx (xx.x%)	xx (xx.x%)
with platelet abnormal result	xx (xx.x%)	xx (xx.x%)	xx (xx.x%)	xx (xx.x%)	xx (xx.x%)	xx (xx.x%)
with one or more abnormal result	xx (xx.x%)	xx (xx.x%)	xx (xx.x%)	xx (xx.x%)	xx (xx.x%)	xx (xx.x%)
with no abnormal result	xx (xx.x%)	xx (xx.x%)	xx (xx.x%)	xx (xx.x%)	xx (xx.x%)	xx (xx.x%)
Visit 2 (Day 8)						
with hemoglobin abnormal result						
with WBC abnormal result						
with platelet abnormal result						
with one or more abnormal result						
with no abnormal result						
Visit 4 (Day 36)						
with hemoglobin abnormal result						
with WBC abnormal result						
with platelet abnormal result						
with one or more abnormal result						
with no abnormal result						

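### Post-vaccination laboratory abnormalities are counted and tested without regard to the screening grade, so persisting pre-existing abnormalities inflate a primary safety endpoint and dilute its group comparison

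*SAP*

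**What the plan says.** **Entry.** The laboratory exclusion in Section 4.2.3 carries no grade limit: "Abnormality in screening laboratory test deemed exclusionary by the PI in consultation with the Sponsor". The inclusion criterion in Section 4.2.2 is also a judgement: "Healthy, as defined by absence of clinically significant medical condition, either acute or chronic, as determined by medical history, physical examination, screening laboratory test results".

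**Endpoint.** The second primary endpoint in Section 3.2.1 is "Number, severity, and relatedness of clinically significant hematological and biochemical measurements at 7 days post each vaccination".

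**Counting.** Section 8.3.1 presents this endpoint as subjects out of range, by toxicity grade, relatedness and group, in Tables 60 through 68. Section 8.6 grades screening, Day 8 and Day 36 values and then states that "Grade 2 or higher were automatically considered as clinically significant and reported as AE, while Grade 1 abnormalities were subject to investigator opinion". It applies a two-tailed Fisher's exact test to abnormality rates across all groups, by scheduled visit and overall. Table 60 has rows such as "with hemoglobin abnormal result" for Overall, Visit 2 and Visit 4; Table 64 does the same for chemistry. Neither has a baseline row or a new-onset split.

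**A definition already in the plan.** Section 3.3.7 calls an event treatment-emergent if it was absent before dosing or, "if present prior to the administration of the study medication, increases in intensity after administration of the study medication".

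**Where baseline appears.** Tables 61 to 68 show the baseline grade distribution and percent change. Listings 9A and 9B show each subject's baseline, Day 8 and Day 36 values.

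**The concern.** The endpoint is meant to describe what happens in the blood tests after each dose. As tabulated and tested, it describes who has an abnormal value on that day. The two differ for anyone who entered with an abnormal value that did not change, and the discretionary exclusion lets such a person in.

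At stake are the absolute rate in each arm, which will be read as a post-vaccination rate, and the ability of Fisher's test to separate a reactive formulation from placebo. Carried-over abnormalities add a similar background to every arm, and that background makes up the larger share in an arm with few new events. Section 4.1 names clinical laboratory results among the parameters for advancing a formulation to Phase 2. Under Section 6.6.1 the interim report takes Tables 60 and 64 but not Tables 24 to 27, 61 to 63 or 65 to 68, which hold the tabulated screening results.

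**Working it through.** **1. The plan's own figure.** The SAP gives no figure for this counting rule. The nearest is in Section 5, the exact upper limit when no event is seen: 1 − 0.025^(1/25) = 13.7% for 25 subjects and 1 − 0.025^(1/150) = 2.4% for 150. Both reproduce.

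**2. One carried-over subject.** 0/25 has an exact 95% interval of 0 to 13.7%. 1/25 = 4.0%, with Clopper-Pearson interval 0.1% to 20.4%.

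**3. How the rule acts on one subject (grades from Table 21).** A woman with hemoglobin 10.8 g/dL at screening is Grade 2 (9.5 to 10.9). If the value is 10.8 at Day 8 and Day 36, she is still Grade 2 with a change of 0. Under Section 8.6 she is clinically significant at both visits, and Table 60 counts her at both. By the logic of Section 3.3.7 nothing has emerged. This is a hypothetical subject, used to trace the rule.

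**4. How often (assumed).** The SAP gives no screening prevalence, so a range is shown. With prevalence p, the expected number per arm of 25 is 25p, and the chance of at least one is 1 − (1 − p)^25.

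| p (assumed) | expected per 25 | expected per 120 | chance of at least one in 25 |
|---|---|---|---|
| 5% | 1.25 | 6 | 72% |
| 10% | 2.5 | 12 | 93% |
| 20% | 5 | 24 | 99.6% |

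**5. Dilution (assumed).** Suppose 80% of screening abnormalities persist at Day 8, and new onset among screening-normal subjects is 30% in an active arm and 2% on placebo. The rate under the plan's count is 0.8p + (1 − p)q, where q is the new-onset rate; the pre-existing share is 0.8p divided by that rate. At p = 10%:

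- active: 0.08 + 0.90 × 0.30 = 0.350, pre-existing share 0.08/0.350 = 23%
- placebo: 0.08 + 0.90 × 0.02 = 0.098, pre-existing share 0.08/0.098 = 82%

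Power below comes from exact enumeration of the two-sided Fisher test at 0.05, 25 active against 20 placebo. The plan tests across all groups; one pair is used here for simplicity.

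| p | pre-existing share, active | pre-existing share, placebo | power, plan's count | power, new onset only |
|---|---|---|---|---|
| 0 | 0% | 0% | 68% | 68% |
| 5% | 12% | 68% | 55% | 64% |
| 10% | 23% | 82% | 44% | 59% |
| 20% | 40% | 91% | 30% | 48% |

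**6. Whether the other displays close the gap.** The McNemar tests in Tables 61 to 63 cover hematology only, are within group, and use normal/abnormal, so a move from Grade 1 to Grade 3 does not register. Chemistry Tables 65 to 68 use a Kruskal-Wallis test and have no paired test of normal/abnormal status. Their change row after Visit 4 repeats the Day 8 label. Baseline and visit grade rows are marginal counts, not subject-level shifts. The hemoglobin and creatinine change criteria in Tables 20 and 21 are joined to the absolute limits by OR, so they can only add abnormalities.

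**The case against.** The case on the other side is substantial, and several parts of it stand.

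- **The AE definition.** A reader might infer that Section 8.6 contradicts Section 3.3.1. It does not: the list there, which mentions worsening of a pre-existing condition, is expressly not exhaustive, and AEs are recorded from consent. Section 3.3.7 defines a separate category and is the firmer anchor. Tables 39 to 41 and 43 count AEs by onset within 28 days of a dose, so an unchanged earlier abnormality need not enter them. The problem lies in the laboratory counts and their test.
- **The interim report.** A reader might infer that interim reviewers cannot see baseline values. They can: Section 6.6.1 includes Listings 7 to 9, and Listings 9A and 9B give them by subject. Carry-over could be worked out by hand among 120 subjects. The summary counts and the test still do not use it.
- **Whether such subjects are expected.** Table 25 ("Abnormality of Hematology Test with Clinically Significant Result at Screening") and Table 27 ("Abnormality of Chemistry Test with Clinically Significant Result at Screening") might be read as showing that they are. Empty shells do not show that: Table 28 likewise has positive rows for hepatitis serology, although positives are excluded. The documents permit such subjects but do not predict them.
- **Bias.** Randomization balances screening abnormalities in expectation. Chance imbalance is possible with 20 to 25 per arm, but no arm is systematically favored.
- **Grade 1 values.** These become clinically significant only by investigator opinion. The automatic rule reaches only subjects enrolled at Grade 2 or higher. The abnormality counts and Fisher's test take in every grade.
- **A naive correction.** Counting only when the grade exceeds the screening grade would hide real declines. A man falling from 12.4 to 10.6 g/dL is Grade 2 at both times by absolute value (10.5 to 12.4), yet the fall of 1.8 g/dL is itself Grade 2 by change (1.6 to 2.0). The fix has to allow for this.

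**Conclusion.** The point holds for the summary counts in Tables 60 and 64, the automatic clinical significance of Grade 2 or higher in Section 8.6, and Fisher's test. None of these conditions on the screening grade, although Section 3.3.7 already supplies the concept. The effect is inflated absolute rates and a diluted contrast between groups in a primary safety endpoint. It is not systematic bias between arms, and the information is not absent from the plan.

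The size depends on how many subjects enter with an abnormal value, which the documents do not give. A single carried-over subject adds 4 percentage points to an arm of 25. At an assumed 5% to 20% screening prevalence, with the other assumptions stated, power falls from 64% to 55% at the low end and from 48% to 30% at the high end compared with counting new onset only. If nobody enters with an abnormal value, the two counts coincide. The change should be made because it is cheap and uses data already collected.

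**What to change.** 1. In Section 8.6, define a treatment-emergent laboratory abnormality consistent with Section 3.3.7. The flag is true when the post-dose grade in a given direction exceeds the screening grade in that direction, with high and low WBC handled separately, or when a change-from-baseline criterion in Tables 20 and 21 (hemoglobin, creatinine) is met. The second condition keeps the fall from 12.4 to 10.6 g/dL in the count.
2. Use this flag for the primary counts in Tables 60 and 64 and for Fisher's test. Show persisting pre-existing abnormalities on a separate line.
3. Add subject-level shift tables of grade from baseline to Day 8 and Day 36 for all seven parameters.
4. Reconcile the automatic Grade 2 or higher wording in Section 8.6 with Section 3.3.7. Leave recorded AEs and Listings 9A and 9B as they are; a derived flag does not reclassify an AE already reported.

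The cost is SAP wording, one derived variable and a set of shift tables. Screening grades are already collected, and all graded values remain listed.
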